8.3. Data Management Procedures

Refer to Annex A.

9. SAMPLE SIZE AND POWER CALCULATION

9.1. Sample Size / Power Calculation

Sample size is limited by the availability of funding to deliver the personalised budgets. We therefore provide the power implications of various attrition scenarios between baseline and a single endline (i.e. the 12-month follow-up).

Under our likely attrition scenario of 25%, our minimum detectable effect size (MDES) at alpha = 0.05 and beta = 0.8 is 0.273, representing a moderate effect size. Owing to the costly nature of the intervention and effect sizes observed in similar studies, we believe this is acceptable.

9.2. Attrition Assumptions

We have assumed a 25% attrition between baseline and endline data collection, as this is similar to the current attrition rate on a similar cash transfer trial conducted by King's College London. This has the effect of reducing the effective sample size to 270 participants and increasing the MDES by 15%. Scenario C in the table below also provides calculations for a more conservative sample with 35% attrition, which leads to a further increase of the MDES to 0.293. However, even with this higher attrition rate, we judge the sample size to be sufficient to detect a relevant effect size given the magnitude of the intervention.

9.3. Software

Power calculations were carried out in the statistical software R.

Table 7: Sample size calculations

	Scenario A	Scenario B	Scenario C
Minimum Detectable Effect Size (MDES)	0.236	0.273	0.293

Pre-test/ post-test correlations	level 1 (participant)	0.6	0.6	0.6
	Alpha	0.05	0.05	0.05
	Power		0.8	0.8
Alternative hypothesis: One-sided or two-sided		Two-sided	Two-Sided	Two-Sided
	Intervention	180	180	180
Number of participants	Control	180	180	180
	Total	360	360	360
Expected attrition at individual level	%	0	25	35
Effective sample (Participants)	Total	360	270	234

10. ANALYTICAL STRATEGY

10.1. Analytic Sample

All Analytic Populations
 Participants will be identified and approached by the charity partners.
 They will be individuals known to the charity partners and assessed as meeting the inclusion criteria and not meeting the exclusion criteria.
 All participants will be over 18 years old, and there is no upper age limit.

[figure not shown]
10.2. Descriptive statistics

The following descriptive statistics will be reported:

- Sample size and attrition at each data collection wave.
- Sample and treatment group characteristics included in the survey (age, gender identity, sexual orientation, ethnicity, nationality and disability).
- Balance achieved across treatment and control by covariate and site, for the full baseline sample, and the sample at each wave. Balance will be reported as absolute numbers/group means, and effect sizes (Cohen's d or Hedges' g, if relevant subsample <20 participants).
- The distribution of the outcomes at each wave.

10.3. Primary Analyses

Analytical approach

Our main analytical approach for our primary analysis is regression analysis, which will be conducted on an intention-to-treat, complete cases basis. For our main housing outcomes, housing stability and perceived housing quality and satisfaction, measured via Residential Time Line Follow Back Inventory and the OMRA tool, we will conduct a linear regression, evaluated at the mean. Formally, this will be an autoregressive (AR-1), model, specified as:

$$Y_{ipt} = \alpha + \beta_1 Y_{ip0} + \beta_2 B_i + \beta_3 X_i + \beta_4 P_p + u_i$$

Where:

 Y_{ipt} is the value of the respective outcome measure (housing stability and perceived housing quality and satisfaction), for participant i at time t (endline in the primary analysis), referred by charity partner p.

 α is a regression constant

 Y_{i0} is the baseline value of the outcome for participant i in charity partner p.

 B_i is a binary treatment indicator set to 1 if participants are treated and zero else.

 X_i is a vector of participant demographic characteristics including gender (operationalised as a trinary variable) and age (operationalised as a categorical variable with 7 values including prefer not to say).

 P_p is a vector of charity partner fixed effects, reflecting that charity partner is a stratification variable.

 u_i is an error term.

This analysis will be conducted with two values of the time indicator, at the midline and endline data collection points, in both cases using the baseline data at time 0 as a control. Uncertainty will be reported through confidence intervals at p-values. We will report the binary indicator of whether the treatment effect is statistically significant, as well as present the p-value continuously and the confidence intervals.

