5.2. Study Design

Study design details

This trial is a parallel randomised controlled trial with randomisation at the level of the individual participant and with data collection at three time points. Randomisation will occur on a 1:1 ratio, with stratification at the level of the charity partner.

Allocation

Randomisation will be conducted by IFF. IFF Research's approach to randomisation for the two-arm RCTs is 1:1 randomisation at the individual level. This will offer the most reliable estimates because, at the point of randomisation, all important factors would be balanced across the intervention and control condition and the effects can be securely attributed to the trial, within standard statistical tolerances.

To account for rolling participant recruitment to the trial, IFF will use a sequential individual randomisation stratified by charity partner, and with blocks of four samples in each block. In each block of four participants, two would be randomly allocated to the treatment group and two would be randomly allocated to the control group. Since we

do not know the exact number of trial participants, and this is subject to change, we do not know how many blocks we will end up with in the trial. The randomisation algorithm is coded into the baseline survey script; participants will be automatically randomised upon submission of the survey.

Once participants are randomised, we will download the data and check that the randomisation has worked as it should statistically. We will then send through the list of unique IDs that have been assigned to each group to Greater Change, so they know who to deliver the treatment to. Greater Change will then inform the charity partner and the charity partner will inform the participants themselves.

Intervention

After being referred by partner charities, participants allocated to treatment will get support from caseworkers to decide on a plan for them to stop them experiencing homelessness. The caseworker and the client define together what they need (e.g. work tools, driver's licence or secure a deposit), and the amount needed (£4,000 on average). When the funds are made available, the caseworker is responsible for purchasing what was defined in the client's plan.

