Where 1{.} is an indicator function that is equal to 1 if its argument is true and 0 otherwise.

Then the outcome variable is regressed on $E(d_i|B_i)$ with an OLS regression of the form:

$$Y_{ipt} = \alpha + \beta_1 Y_{ip0} + \beta_2 E(d_i | B_i) + \beta_3 X_i + \beta_4 P_p + u_i$$

Where the CACE estimator is β_2

Outcome imputation

We anticipate attrition between baseline, midline and endline data analysis. We will conduct missing data analysis as described below in 10.9, but given that every participant will complete the baseline survey, we primarily expect attrition in terms of outcomes, which will not be imputed under the missing data analysis. However, we will include sensitivity analysis which imputes outcomes between the two post-treatment data points where participants have missing data for one of these points but not the other. As such, if someone is missing data from midline but completes the endline data collection, we will impute their midline outcome measure as their endline outcome, and vice versa.

If exploratory analysis of the missingness mechanism satisfies the MAR assumption, the imputation of these points will be conducted with a dataset that incorporates all three time points to allow for the maximisation of all observed information in the process of imputation.

Following imputation, analysis will be conducted as previously described, for each post-treatment time point separately.

 For the main analyses, our primary outcome measure will be how many days out of the 360 after randomisation that a person is in secure accommodation. This measure will combine the measurement

taken at six months (midline) and that at 12 months, each of which will capture the prior 180 days. When someone completes the endline data but not the midline, they will be asked to recall the last 360 days. As a sensitivity analysis, we will conduct analysis just using the 180 days prior to the endline data collection as an outcome measure.

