10.9. Missing data

Description of Missing Data Patterns

The issue is that those who do not respond to the surveys at endline are likely to be different to those who do, i.e., cases are likely to be either Missing at Random (MAR), if all missingness is correlated to observable covariates, or Missing Not At Random (MNAR), if missingness is correlated with unobservable factors.

Identification of the missingness pattern will be achieved by regressing all available covariates on the likelihood of missingness using a binary logistic regression to see whether covariates predict missingness on outcomes, as specified in the CHI Guidance. If covariates predict missing outcome data well, this suggests that the outcome is MAR .

Where reasons for missingness are known and imply the data are Missing Completely at Random (MCAR), we will conduct complete case analysis.

Handling Missing Data

Our main analysis will be on the basis of complete cases. However, it is likely that there will be greater than 5% attrition for the post-treatment survey waves, which will impact statistical power and

also mean that in some cases we may be comparing outcomes from different samples (e.g. if people who do not respond at 6 months then respond at 12 months and vice versa). This is in line with CHI's statistical guidance.

We will therefore rerun the analysis with missing outcomes imputed. As previously stated, if covariates predict missing outcome data well, this suggests that the outcome is MAR. In this instance, we will add outcomes at previous time points as auxiliary variables, alongside any covariates predictive of missingness into the analytical specification and re-run the analysis, comparing the treatment estimate with the analysis as specified, and the analysis with additional covariates and past outcomes that predict missingness included. If outcomes are MNAR, then neither complete case nor imputation is likely to yield unbiased estimates of the treatment effect. In this case, we will run a range of imputation models, including multiple imputations within the treatment condition and the last observation carried forward (LOCF) and report on how much the treatment estimate changes across different imputation approaches.

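### The primary analysis of secure days out of 360 drops participants seen at midline but not at endline, although half their outcome is recorded

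*Protocol*

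**What the plan says.** Section 7.1 defines the main outcome as days in secure accommodation out of the 360 after randomisation. The end of section 10.6 says how it is built: a midline and an endline report, each covering the preceding 180 days. It adds: "When someone completes the endline data but not the midline, they will be asked to recall the last 360 days". There is no matching rule for someone who completes midline but not endline.

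Section 10.3 sets the primary regression, "which will be conducted on an intention-to-treat, complete cases basis", with baseline outcome, gender, age and charity partner as covariates. Section 10.9 repeats: "Our main analysis will be on the basis of complete cases". The same section says that "those who do not respond to the surveys at endline are likely to be different to those who do", and expects the data to be missing at random (MAR) or not at random (MNAR).

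Midline data on endline non-responders are used in three other places:
- the separate midline analysis (10.3, 10.8);
- the 10.6 sensitivity analysis, which carries a value between the two follow-up waves, or uses all three waves if MAR is accepted;
- the 10.9 reruns, which under MAR add outcomes from previous time points to the model specification, and under MNAR include multiple imputation within arm and last observation carried forward.

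**The concern.** The handling is asymmetric. A missing first half is recovered by a longer recall; a missing second half removes the participant from the headline estimate, including a first half already collected. The covariates in 10.3 do not include housing status at six months, which could well predict both losing contact and the second-half days. The reported estimate, p-value and significance verdict would therefore describe people still reachable at 12 months, in a trial whose sample size is limited by funding (9.1).

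The MAR rerun in 10.9 raises a second problem. Baseline outcome is already in the 10.3 model, so at endline the only earlier outcome left to add is midline. First-half days are affected by treatment and are a component of the 360-day total. Adjusting for them in the regression removes part of the effect being estimated.

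**Working it through.** **Inputs from the protocol.** Section 9.1: "our minimum detectable effect size (MDES) at alpha = 0.05 and beta = 0.8 is 0.273" (0.8 is the power; Table 7 lists it as such). Table 7: two-sided in all scenarios, row "Alternative hypothesis: One-sided or two-sided"; correlation 0.6, row "Pre-test/ post-test correlations"; 25% attrition, so 270 of 360 remain. Section 5.2: "Randomisation will occur on a 1:1 ratio".

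**Assumptions, not in the protocol.** f is the share of endline non-responders who completed midline, 0.4-0.75 (wider 0.25-1.0). r is the correlation between the two 180-day halves, 0.5-0.7 (wider 0.3-0.9). The halves have equal variance and equal correlation with baseline, and outcomes are treated as normal.

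**1. The plan's own figures.** MDES = (1.960 + 0.842) × √(1 − 0.6²) × √(4/N), with √(1 − 0.36) = 0.8.
- N = 360: 0.2363 (stated 0.236)
- N = 270: 0.2728 (stated 0.273)
- N = 234: 0.2930 (stated 0.293)

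All three reproduce. Complete-case power at N = 270 and 0.273 SD is 80.1%.

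**2. Power when the midline half is used.** The share of outcome variance, given baseline, explained by the first half is R² = 0.32(1 + r)/(1 − 0.18(1 + r)). That is 0.48/0.73 = 0.658 at r = 0.5 and 0.544/0.694 = 0.784 at r = 0.7. With n = 270 and k = 90f, Var(effect) = 4 × 0.64 × [(1 − R²)/n + R²/(n + k)].
- f = 0.4, r = 0.5: k = 36; effective N = 1/(0.342/270 + 0.658/306) ≈ 293; power 83.2% (+3.1 points).
- f = 0.75, r = 0.7: k = 67.5; effective N = 1/(0.216/270 + 0.784/337.5) ≈ 320; power 86.3% (+6.2).
- f 0.25-1.0, r 0.3-0.9: +1.6 to +9.1. With no missing data, power would be 89.9%.
- 35% attrition, effect 0.293: +5.5 to +6.6 at f = 0.5 and r 0.5-0.7; +2.5 to +12.6 over the wider inputs.

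A simulation of 6,000 trials with attrition unrelated to outcome and f = 0.5 gave 77.9% → 82.3% (r = 0.5) and 80.5% → 85.0% (r = 0.7), with both estimates essentially unbiased.

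**3. Bias, by simulation (true effect 0.273).** The first two cases come from 1,500 trials per scenario, with attrition depending on first-half days, r 0.6-0.8, f 0.4-0.6, and the effect split 40/60 over the halves.
- Similar attrition in both arms: complete-case bias about 0-4%. The 6,000-trial simulation, with a stronger fixed dependence and an even split of the effect, gave 0.259 and 0.258, or 5-6% too small; using midline gave 0.267-0.268.
- Attrition of about 20% intervention and 30% control: complete-case 0.224-0.245 (10-18% too small); with midline-based imputation 0.252-0.265 (3-8% too small).
- Extreme case, dropout tied to first-half days in controls only (6,000 trials): complete-case about 0.17; using midline about 0.23.

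Monte Carlo error in the 1,500-trial figures is about 0.10/√1,500 = 0.0026, so each percentage is uncertain by about 2 points either way.

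**4. Midline inside the regression.** Let s be the share of the effect falling in the first half (assumed 0.4-0.5), and c² = 0.36(1 + r)/2 the squared correlation of each half with baseline. With no missing data, adjusting for midline leaves 0.273 × [1 − s(1 + (r − c²)/(1 − c²))].
- r = 0.5: bracketed slope 1 + 0.23/0.73 = 1.315; 0.129 (s = 0.4) or 0.093 (s = 0.5).
- r = 0.8: slope 1 + 0.476/0.676 = 1.704; 0.087 or 0.040.

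The true 0.273 would appear as about 0.04-0.13.

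**The case against.** A reader might infer that the midline data are thrown away. They are not: the midline analysis uses them, 10.6 and 10.9 rerun the endline analysis with them, and imputation within arm is already named. Section 10.9 also describes complete-case as in line with the funder's guidance, which cannot be examined here. So the dispute is over which analysis carries the headline.

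That stands, but it does not dispose of the point. The reruns do not alter the primary estimate or its significance verdict. Within-arm multiple imputation is named only for the case in which the protocol says imputation is unlikely to be unbiased. Section 10.6 says outcomes will not be imputed under 10.9, whereas 10.9 says they will.

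A reader might also infer that the complete-case estimate is materially biased. The documents do not establish this. Bias above 10% required an assumed difference in attrition between arms. Both arms keep the same usual caseworker support (4.1), and the tracing and vouchers in 8.2 make no distinction by arm. Even the direction is uncertain, since intervention participants who move on could lose contact too. Nor would imputation cure MNAR or inform on people who miss both waves.

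**Conclusion.** The point holds for the 360-day outcome as a worthwhile, inexpensive improvement to the primary analysis. At 25% attrition the complete-case choice gives up about 3-6 points of power under central assumptions and about 2-9 over wider ones. These are conditional figures, because f and r are not in the protocol; if most endline non-responders also missed midline, the gain is near the bottom of the range. They also treat a bounded count of days as normal. Complete-case bias is about 0-4% with similar attrition by arm (5-6% in the harsher simulation) and about 10-18% under the assumed 20% versus 30% split; imputation reduces but does not remove it.

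The half-observed argument should not be extended to perceived housing quality and satisfaction, which asks about current housing (Annex C), or to the secondary outcomes. There midline is only an auxiliary variable. The warning against putting midline into the regression is independent of f, though the size of the shrinkage depends on r and on how the effect divides between the halves.

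**What to change.** - In 10.3 and 10.9, for the 360-day outcome, make the primary estimate the 10.3 regression after multiple imputation done separately by arm. The imputation model should hold the baseline covariates, baseline outcome and midline housing days. For midline-only participants, keep the observed first 180 days and impute only the second 180.
- In 10.9, state that midline outcomes enter the imputation model and never the endline analysis regression.
- Report the complete-case result as a sensitivity analysis, and keep the MNAR analyses.
- Reconcile Table 6, which lists only secondary outcomes at midline, with 7.1, 10.6 and Annex B, which collect housing history then. The fix depends on that record.
- For housing satisfaction and the secondary outcomes, using midline as an auxiliary in imputation is optional.

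The cost is protocol wording and analysis code, with no new data; 13.2 already provides for an addendum before analysis. The downside is that the headline then rests on a stated MAR imputation model and departs from the complete-case approach described as in line with the funder's guidance.

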5.3. Research Setting

The research will take place in a number of settings throughout England, covering the South West, South East, London, the Midlands and the North East. These regions have been selected via a competitive expression of interest process to ensure some generalisability and scalability of results. All participants will be resident in temporary accommodation at the time of their recruitment to the trial, and receiving support from one of the charity partners recruited for the trial. Participants will be surveyed over the phone or online for data collection.

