- 12. Accommodation linked to your work or studies, for example student accommodation, military accommodation or accommodation linked to a business.

1b. When did you start living there? (best guess)

(day/month/year)

[Note: This should be a best guess. The interviewer could also prompt by asking about time of year the person lived there.

A suggestion used in previous studies is to have a calendar with days and month for participants to work backwards from where they are currently living.]

1c. Roughly, how long have you stayed there [did you stay there]? (best guess)

Number in (months) + (weeks) + (days)

[Note: This should be a best guess. The person does not need to fill in the three levels]

1d. Have you stayed in any other accommodation in the last 6-months?

Yes, No

[If yes, jump back to 1.a]

Source: Modified version of the Residential Timeline

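### The primary model names few baseline adjusters, the 0.6 baseline correlation is unsupported for the day count, and plausible predictors already collected enter only in a conditional re-run

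*Protocol*

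**What the plan says.** Section 10.3 sets out the regression in full: baseline value of the outcome, treatment, X and charity partner fixed effects, by intention to treat on complete cases. X "is a vector of participant demographic characteristics including gender (operationalised as a trinary variable) and age". Gender has three levels and age seven. The same model serves both joint primary outcomes: days in secure accommodation out of 360, and perceived housing quality and satisfaction.

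On the baseline housing state, section 5.3 says: "All participants will be resident in temporary accommodation at the time of their recruitment to the trial". Section 6.1 repeats this as an inclusion criterion and sets no minimum stay. Annex B looks back six months and records accommodation type, start date and duration ("Roughly, how long have you stayed there [did you stay there]? (best guess"). Annex F records employment at baseline. Section 10.2 lists the survey characteristics as "age, gender identity, sexual orientation, ethnicity, nationality and disability".

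On power, section 9.1 states that the MDES "at alpha = 0.05 and beta = 0.8 is 0.273, representing a moderate effect size" (the figure labelled beta is the power). Table 7 enters 0.6 in the row "Pre-test/ post-test correlations" for all three scenarios.

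On missing data, section 10.9 keeps complete cases for the main analysis. If missingness looks at random, a re-run adds past outcomes "alongside any covariates predictive of missingness into the analytical specification". If it does not, several imputation models are compared. Missing covariates are also handled by complete-case analysis.

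**The concern.** Section 9.1 says that funding for the budgets limits the sample size, so power cannot be bought with more participants. Baseline adjustment is the cheapest source of precision left, and the plan relies on it: the stated MDES assumes that the baseline value explains 36% of outcome variance (0.6²). For the day count that is doubtful. Eligibility puts everyone in the same broad housing state on the day of recruitment, and a baseline measure with little spread usually predicts little.

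The survey meanwhile holds other baseline values that plausibly predict moving on: recent rough sleeping, time in the current place, type of accommodation and paid work. The main model names none of them, and the description of X as demographic does not naturally cover housing history or employment.

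Section 10.9 itself expects endline non-responders to differ from responders, and section 9.2 expects 25% attrition. Covariates that predict both outcome and dropout are the ones that make a missing-at-random assumption credible. In this plan they can enter only after their relation to missingness has been inspected, and then only in a re-run that leaves the main estimate unchanged.

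**Working it through.** **Inputs.** Two-sided alpha 0.05, power 0.80, correlation r = 0.6, 360 randomised 1:1, 270 analysed at 25% attrition and 234 at 35% (sections 9.1–9.3, Table 7).

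**1. The plan's own figures.** MDES = (1.960 + 0.842) × √(1 − r²) × √(4/N). With r = 0.6 this gives 0.2363 at N = 360, 0.2728 at 270 and 0.2930 at 234, against the stated 0.236, 0.273 and 0.293. They reproduce, so the stated precision depends directly on r = 0.6.

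**2. If the baseline day count predicts less (N = 270).**

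| r | MDES | Power at 0.273 | Analysed N for 80% power at 0.273 |
|---|---|---|---|
| 0.6 | 0.273 | 80% | 270 |
| 0.3 | 0.325 | 65% | 384 |
| 0.2 | 0.334 | 63% | 406 |
| 0 | 0.341 | 61% | 422 |

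At r = 0.3 or below, the required number exceeds the 360 to be randomised.

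**3. How restricted could the baseline be?** The protocol does not say. As an illustration, suppose temporary accommodation is not secure and a share q of participants had some secure days, uniform on 0–180. The variance is then 10,800q − 8,100q². For q = 5% the SD is √(540 − 20.25) = 22.8 days; for q = 30% it is √(3,240 − 729) = 50.1 days. The count is skewed with a mass at zero, but not constant.

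**4. What added covariates could recover.** The documents give no explained variance for them, so 5%, 10% and 20% of residual variance are assumptions. MDES at N = 270, before the degrees-of-freedom cost:

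| Starting r | 5% | 10% | 20% |
|---|---|---|---|
| 0 | 0.332 | 0.323 | 0.305 |
| 0.3 | 0.317 | 0.309 | 0.291 |
| 0.6 | 0.266 | 0.259 | 0.244 |

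**5. Cost in degrees of freedom.** The current model uses about 20 parameters: intercept 1, treatment 1, baseline 1, gender 2, age 6, and 9 for the ten partners listed in Table 5. That leaves 270 − 20 = 250. Five single-parameter covariates (the four plus disability) multiply the variance by (1 − R²) × (1 + 5/250):

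- R² = 5%: 0.95 × 1.02 = 0.969, a 3% fall, worth 270 × (1/0.969 − 1) ≈ 9 participants.
- R² = 10%: 0.90 × 1.02 = 0.918, an 8% fall, worth about 24.
- R² = 20%: 0.80 × 1.02 = 0.816, an 18% fall, worth about 61.

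With a missing-indicator for each covariate the cost could reach ten parameters. The multipliers are then 0.95 × 1.04 = 0.988, 0.90 × 1.04 = 0.936 and 0.80 × 1.04 = 0.832, so the gain at 5% nearly vanishes.

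**The case against.** The planned model is conventional: baseline outcome, stratification factor, age and gender. Covariate lists are often completed in a statistical analysis plan, which is not at hand. X is also worded as an open list. That has weight, but the protocol does write out the equation and limit X to demographics, and an open list in the primary model leaves a choice that should be closed. If the analysis plan already closes X with housing history and employment, the covariate part of this point is answered.

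A reader might infer that eligibility makes the baseline day count nearly constant. The documents do not support that. Eligibility fixes the state on one day, the look-back is six months, and *secure* is undefined. If temporary accommodation counted as secure, the baseline count would already carry much of the rough-sleeping information. Accommodation type is restricted by the same rule and helps only if eligible participants span more than one Annex B category. Nor does the restriction reach the satisfaction score, whose baseline eligibility does not constrain.

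A reader might also infer that the omission biases the main estimate. It does not bias the randomised comparison in full data. Bias needs dropout that differs by arm on these variables. With 25% dropout in both arms, a 0.2 SD gap between completers requires the dropouts to differ by 0.2 × 0.75/0.25 = 0.6 SD, and nothing in the protocol suggests that.

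Protection against dropout is not absent either. Sections 10.6 and 10.9 plan past outcomes as auxiliaries and several imputations, and section 10.2 reports balance at each wave. These remain conditional or secondary analyses.

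Last, timing: version 2.0 is dated 17 June 2025, and the interim report, under the current model, was due in July 2025. A change now needs a documented amendment.

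**Conclusion.** The point holds as one of efficiency and specification. The primary model names no non-demographic predictor apart from the baseline outcome and partner. The 0.6 correlation has no stated basis for the day count, and eligibility makes it doubtful without showing that it is near zero. If r were between 0 and 0.3, the MDES at 270 analysed would be about 0.325–0.341 instead of 0.273.

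Pre-specified covariates could recover part of that: about 3–18% of variance if they explain 5–20% of the residual, which is an assumption and not a figure from the protocol. Starting from r = 0, even the top of that range (0.305) does not return to 0.273. The second benefit, a more plausible missing-at-random assumption for the complete-case estimate, cannot be quantified from the document.

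**What to change.** Before endline data are unmasked, close X in section 10.3 as a short pre-specified list. Keep baseline outcome, gender, age and partner. For the day-count outcome add days slept rough in the prior six months, length of current stay, accommodation type and paid work (yes/no), with disability optional. State which Annex B categories count as secure, so that the overlap between the baseline count and days slept rough can be judged.

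Handle missing baseline covariates by a missing-indicator or simple imputation, and amend the complete-case rule for covariates at the end of section 10.9 to match. Simple imputation spares parameters.

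Report the current specification as a sensitivity analysis, including the midline analysis specified under it in section 10.8. In section 9, give the basis for 0.6 or show the MDES for the day count over lower correlations.

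The cost is a handful of degrees of freedom out of about 250 and a documented amendment. No new data are needed.
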